# **Abstract**

**Background and Aims:** Vitamin D deficiency is common in patients with chronic hepatitis B virus (HBV) infection. Previous study showed an inverse association between vitamin D and HBV DNA levels. However, the causal relationship between vitamin D and HBV replication remains inconclusive.

Methods: HBV carriers receiving regular 6-month surveillance without current antiviral treatment or cirrhosis were invited to participate into this trial. The markers of HBV replication included serum HBV DNA and quantitative HBsAg (qHBsAg) levels. Those with undetectable HBV DNA or sufficient vitamin D levels, cancer or electrolyte imbalance were excluded. The eligible subjects were randomized to receive either vitamin D supplement 2000 IU per day for 2 months (vitamin D group) or none (control group). Levels of vitamin D, HBV DNA and qHBsAg before and after 2 months of treatment or follow-up were compared between these two groups. The primary endpoint was to identify any difference between two groups.

# Introduction

Hepatitis B virus (HBV) infection is a global health problem, especially in Taiwan. The clinical manifestations of HBV infection include acute/fulminant hepatitis or various forms of chronic infection. Chronic HBV infection may lead to inactive carrier, chronic hepatitis, liver cirrhosis, or hepatocellular carcinoma (HCC). Low vitamin D is frequently found in patients with chronic hepatitis B (CHB) than healthy controls. Furthermore, several cross-sectional studies showed an inverse association between serum vitamin D level and HBV DNA level. However, the causal relationship cannot be confirmed from these studies.

Cholecalciferol is the precursor of the bioactive vitamin D. It is rare in natural foods and the major source is synthesized in the skin during exposure to sunlight. It is hydroxylated in liver to calcidiol, which is released into the plasma and exerts its biological functions by signaling through a nuclear vitamin D receptor. Therefore, liver has a close relationship with the synthesis of vitamin D. Vitamin D plays a crucial role in the bone metabolism and affect immune function not only in innate but also in adaptive immunity. In clinical practice, low vitamin D is associated with autoimmune, infective disease, and the development of malignancy.

Vitamin D has been reported to be an important immune modulator of hepatitis C virus (HCV) infection and metabolic liver disease. 15-20 Regarding HBV-infected patients, the relationship among vitamin D level, HBV viral load and liver dysfunction remains largely unclear. To clarify the causal relationship, we conducted a randomized controlled trial of providing vitamin D supplement to HBV patients with insufficient vitamin D (<30 ng/mL) level to investigate the effect of vitamin D level on HBV replication in terms of HBV DNA and qHBsAg levels.

#### **Materials and Methods**

#### Patients and study design

This was a randomized controlled trial. The sample size was determined using two samples t-test power calculation. The 1 log increase of serum HBV DNA level was defined as a significant difference between two samples. Effect size (Cohen'd=0.39) was obtained using two parameters including difference and standard deviation. The power and a significant level were set as 0.8 and 0.05, respectively. The sample size was calculated out as 82 in each group. The ratio of exclusion was estimated as 20 %. Therefore, the sample size was set as 196 in this clinical trial. In our clinical experience, the majority of vitamin D deficiency patients can achieve adequate serum vitamin D levels after two months vitamin D supplement. Furthermore, the liver dysfunction due to hepatitis flare or cirrhosis could be a confounding factor for the low serum vitamin D levels in HBV-infected patients. According to the above consideration, our study was designed to enroll 196 non-cirrhotic, HBV-infected patients with normal or minimally elevated serum ALT levels. Thus, chronic HBV patients receiving regular 6-month surveillance and without current antiviral treatment in the outpatient clinic of Taipei Tzu Chi Hospital were invited to join the study from

August 2017 to September 2018. All had positive hepatitis B surface antigen (HBsAg) for more than 6 months. Those with positive anti-hepatitis C virus (HCV) antibody, alcoholic liver disease, other known causes of chronic hepatitis or hepatocellular carcinoma were excluded. Cirrhosis was diagnosed based on histological findings or ultrasonographic evidence of nodular liver surface with coarse echotexture and splenomegaly. After obtaining written informed consent, levels of serum vitamin D, HBV DNA and quantitative HBsAg (qHBsAg) levels were measured. Those who had HBsAg loss, undetectable HBV DNA and adequate vitamin D level (≥30 ng/mL) were excluded. The eligible subjects were randomized into two groups by using the computer random distribution. Patients in the vitamin D group received vitamin D supplement (D3, 2000 IU/day; Metagenics, Aliso Viejo, CA 92656) for 2 months and untreated patients were used as the control group. Levels of vitamin D, HBV DNA and qHBsAg before and after 2 months of treatment or follow-up were compared between these two groups. The primary endpoint was to identify any difference between two groups. Patients lost to follow-up or poor drug compliance (vitamin D intake amount < 80%) were excluded for per-protocol analysis. Both intention-to-treat and per-protocol analyses were conducted.

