# Quantification of HBV DNA and HBsAg levels

Serum HBV DNA level was quantified using Roche COBAS AmpliPrep/COBAS TaqMan HBV Test (Roche Molecular Systems, Inc, USA). The lower limit of quantification was 20 IU/ml. Serum qHBsAg level was assayed using the Architect HBsAg QT (Abbott Laboratories) according to the manufacturer's instruction. The detection range is from 0.05 to 250 IU/ml. If the qHBsAg level was found to be higher than 250 IU/ml, the samples were 1:100 or 1:1000 diluted to obtain a reading within the range of the calibration curve.

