Title: The causal relationship between serum vitamin D level

and hepatitis B virus replication in patients with chronic

hepatitis B virus infection

NCT 03068767

Date of document: 1, June 2017

IRB approval letter (as attached)

Statistical Analyses Plan

Statistical analysis was performed using SPSS version 16.0 (SPSS Inc. Chicago, IL).

Data were analyzed by chi-square test and student's t test. The correlation among

serum vitamin D and FIB-4 was analyzed using Pearson's correlation analysis. The

significance in all of the tests was two-tailed and a p value of less than 0.05 was

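### The 82 per group fits only a one-sided test; under the SAP's two-tailed rule the plan's own effect size has about 70% power, not 80%

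*Protocol*

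**What the plan says.** The sample-size paragraph of the Protocol (Patients and study design) names the method: "The sample size was determined using two samples t-test power calculation". It sets the target: "The 1 log increase of serum HBV DNA level was defined as a significant difference between two samples". It then gives the standardised effect: "Effect size (Cohen'd=0.39) was obtained using two parameters including difference and standard deviation". Error rates follow: "The power and a significant level were set as 0.8 and 0.05, respectively". The result is 82 per group, raised to 196 in total for an expected 20% exclusion.

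The paragraph does not say whether the 0.05 is one-sided or two-sided. It prints no SD, gives no source for one, and does not say whether the SD belongs to the HBV DNA level or to its change over two months. The same section describes the comparison only as: "Levels of vitamin D, HBV DNA and qHBsAg before and after 2 months of treatment or follow-up were compared between these two groups".

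The SAP names Student's t test and the chi-square test, and settles sidedness for the analysis: "significance in all of the tests was two-tailed and a p value of less than 0.05 was" (the sentence breaks off there in the text available).

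**The concern.** This paragraph is the plan's only statement of what the trial can detect. A sample size calculated for a one-sided test and then analysed two-sided does not deliver the power it claims. If that happened here, the 80% figure is wrong on the plan's own inputs, whatever the true variability.

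A second doubt comes from the missing SD. A 1-log difference with d = 0.39 fixes the SD at 2.56 log. That is a wide spread, and it would be surprisingly large for a two-month change in untreated patients selected for normal or minimally elevated ALT. Since the plan does not name the tested quantity, a reader cannot tell what difference in log units the trial can resolve.

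**Working it through.** **Inputs.** From the Protocol (Patients and study design): difference 1 log (base not stated, log10 assumed), d = 0.39, power 0.80, level 0.05, 82 per group, 196 in total. From the SAP: two-tailed tests. Equal allocation is assumed, so 196/2 = 98 per group.

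**Implied SD.** SD = difference/d = 1/0.39 = 2.56 log. Rounding of d (0.385 to 0.395) gives 2.60 to 2.53.

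**Reproducing 82.** The normal approximation is n per group = 2(z_alpha + z_power)²/d², with d² = 0.1521.

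- One-sided 5%: 2 × (1.645 + 0.842)²/0.1521 = 81.3, so 82. The noncentral-t calculation gives 81.98, so 82.
- Two-sided 5%: 2 × (1.960 + 0.842)²/0.1521 = 103.2, so 104. The noncentral-t calculation gives 104.2, so 105.

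The plan's figure matches the one-sided calculation exactly. Rounding of d does not rescue the two-sided one: even at the upper rounding limit, d = 0.395, it needs 101.6 per group.

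**Power under the SAP's test.** Approximately, power = Φ(d√(n/2) − 1.960).

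| Per group | d√(n/2) | Normal approximation | Noncentral t |
|---|---|---|---|
| 82 | 0.39 × 6.403 = 2.497 | Φ(0.537) = 0.704 | 0.699 |
| 98 | 0.39 × 7 = 2.730 | Φ(0.770) = 0.779 | 0.775 |

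The 98 row applies only if nobody is excluded.

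**What 82 per group does detect.** At two-sided 5% and 80% power the noncentral-t solution is d = 0.440. At the implied SD this is 0.440 × 2.564 = 1.13 log.

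**How this depends on the SD.** The detectable difference is 0.44 × SD. Apart from the last row, the SDs below are assumptions; the documents give none.

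| SD (log) | Detectable difference, 82 per group (log) | Two-sided power for 1 log |
|---|---|---|
| 0.5 | 0.22 | above 99% |
| 1.0 | 0.44 | above 99% |
| 1.5 | 0.66 | 99% |
| 2.0 | 0.88 | 89% |
| 2.56 (implied) | 1.13 | 70% |

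**Level or change.** If 2.56 is the SD of the level, the SD of change is 2.56 × √(2(1 − ρ)), where ρ is the assumed before-after correlation. This gives 1.62, 1.15 and 0.81 log at ρ = 0.8, 0.9 and 0.95. Multiplying by 0.44, the detectable differences in change are 0.71, 0.50 and 0.36 log. The choice of tested quantity therefore matters as much as sidedness.

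**The case against.** **The one-sided calculation may have been intended.** The target is worded as an increase, which has a direction, and the sample-size paragraph never claims to be two-sided. That is a fair reading of how 82 arose. It does not remove the mismatch: the SAP applies two tails to all tests, and the Protocol's primary endpoint is any difference between the groups.

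**The trial may have more power than stated.** If the tested quantity varies less than 2.56 log, power for 1 log rises, reaching 89% at an SD of 2.0 even two-sided. This stands. The 70% figure describes the plan's own effect size and is not a forecast for the trial. It also stands that a null result would be read from its confidence interval, which uses the observed SD and not the planning SD.

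**A stronger reading.** A reader might infer that 2.56 log cannot be the SD of a two-month change, and that the power statement is wrong for that reason. As a change SD under rough normality it would put 95% of changes within ±1.96 × 2.56 = ±5.0 log, which invites disbelief. The documents do not carry the argument that far. They contain no data on HBV DNA variability and never say that the SD is of a change. As the SD of levels, 2.56 can be approached. Entry does not exclude HBeAg-positive patients, so a two-hump distribution is possible. With assumed humps at 8.0 and 3.2 log10, SDs of 1.0 and 1.2, and 30% of patients in the upper hump, the SD is √(0.3 × 0.7 × 4.8² + 0.3 × 1.0² + 0.7 × 1.2²) = 2.48. Nor can a firm floor of 1.3 log10 be used against this. For the assay the Protocol says "The lower limit of quantification was 20 IU/ml", but entry excludes undetectable DNA, which need not be the same threshold.

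**Conclusion.** The stated 80% power for a 1-log difference does not hold for the test the SAP prescribes. On the plan's own d = 0.39, two-sided power is about 70% with 82 per group and about 78% with all 98. With 82 per group, 80% power corresponds to d = 0.44, or 1.13 log at the implied SD; keeping d = 0.39 would take 105 per group. This conclusion needs only the printed inputs and the SAP's two-tailed rule. The conversion to log units also assumes log10 and the implied SD.

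That the SD is too large for a two-month change is a reasonable doubt which the documents do not prove. If the change is tested and its SD is between 0.5 and 1.5 log (assumed), the detectable difference is 0.22 to 0.66 log and the 1-log statement is conservative. The text therefore supports neither a claim that the trial is underpowered for whatever it will test nor a claim that it is overpowered.

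**What to change.** Leave enrolment unchanged. In the Protocol's sample-size paragraph, replace the statement of 80% power for 1 log with: *82 per group detects 0.44 × SD with 80% power, two-sided 5%*. At the implied SD of 2.56 log, add that this is 1.13 log, and that power for 1 log is about 70%.

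In the same sentence, say whether the tested quantity is the month-2 level or the two-month change in log10 HBV DNA. Give the SD of that quantity, with its source or a label that it is assumed. Clinic records may not supply the SD of a two-month change, because the Protocol describes six-monthly surveillance. In that case a short range of SDs, each with its detectable difference, would serve.

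The cost is a rewording, with no added patients and no change to the test. The downside is that the stated power at the plan's own effect size becomes less favourable.

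### The 82 per group matches a one-sided calculation, but the SAP tests two-tailed at 0.05, so power at that size is about 70%, not 80%

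*Protocol*

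**What the plan says.** The sizing is in the Protocol, under Patients and study design. The method is a comparison of two independent means: "The sample size was determined using two samples t-test power calculation". The target is a difference of 1 log in HBV DNA: "The 1 log increase of serum HBV DNA level was defined as a significant difference between two samples". The standardised effect follows: "Effect size (Cohen'd=0.39) was obtained using two parameters including difference and standard deviation". The standard deviation behind it is not printed. The error rates and the result are "The power and a significant level were set as 0.8 and 0.05, respectively. The sample size was calculated out as 82 in each group". A 20% allowance for exclusions then takes the total to 196, or 98 per group if allocation is equal. Sidedness is not mentioned anywhere in that paragraph.

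The SAP names Student's t test for the analysis and settles the sidedness: "significance in all of the tests was two-tailed and a p value of less than 0.05 was" (the sentence breaks off there in the available text). Neither document mentions a one-sided test. The primary endpoint, in the Abstract and in the design section, is worded without a direction, which agrees with the SAP.

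**The concern.** A standardised effect of 0.39 with 80% power and a two-sided 0.05 level should need a little over 100 patients per group, so 82 looks too small. If the size was worked out for a one-sided test and the analysis is two-tailed, the trial was sized for a different test from the one it will run.

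The error does not affect the false-positive rate, because the two-tailed test is valid at 0.05. It affects how a null result is read. The trial is meant to clarify a causal question that cross-sectional studies left open. A reader who sees a non-significant HBV DNA comparison would assume a 20% chance of having missed the planned effect, when at the calculated size the chance is about 30%.

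**Working it through.** **Inputs.** Protocol, Patients and study design: two-sample t-test, d = 0.39, power 0.80, level 0.05, n = 82 per group, total 196, exclusion allowance 20%. SAP: Student's t test, two-tailed, 0.05. The SD is not needed for the check because d is given.

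**Formulas.** The normal approximation for n per group is n = 2(z_α + z_β)² / d², with z_β = 0.8416 for 80% power, z_α = 1.6449 one-sided and z_α = 1.9600 two-sided. Power at a given n is approximately Φ(d√(n/2) − z_α). The exact version uses the noncentral t distribution with 2n − 2 degrees of freedom and noncentrality d√(n/2).

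**Step 1: reproduce the plan's figure.**
- One-sided: 2 × (1.6449 + 0.8416)² / 0.39² = 2 × 6.183 / 0.1521 = 81.3, so 82. Exact t: 81.98, so 82. Exact one-sided power at 82 is 80.0%. The figure reproduces.
- Two-sided: 2 × (1.9600 + 0.8416)² / 0.1521 = 2 × 7.849 / 0.1521 = 103.2, so 104. Exact t: 104.18, so 105. The figure does not reproduce.

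**Step 2: power under the SAP's test, d = 0.39, two-sided 0.05.**

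| Analysed per group | Situation | Normal approximation | Exact t |
|---|---|---|---|
| 82 | the calculated size | Φ(2.497 − 1.960) = 70.4% | 69.9% |
| 98 | all 196 analysed | Φ(2.730 − 1.960) = 77.9% | 77.5% |
| 78 | 196 less 20%: 156.8 / 2 = 78.4 | Φ(2.436 − 1.960) = 68.3% | 67.7% |

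None of the three reaches 80%. The last row arises because 196 matches 82 × 1.2 × 2 = 196.8 rounded down, so losing 20% of 196 leaves fewer than 82 per group.

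**Step 3: what 82 per group can detect.** The effect with 80% two-sided power at 82 per group is d = 0.440. The implied SD is 1 / 0.39 = 2.56 log, so this is 0.44 × 2.56 = 1.13 log.

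**Step 4: other explanations for 82.**
- Rounding of d: values from 0.385 to 0.395 need 107 down to 102 per group two-sided (exact t).
- A paired or one-sample t-test: 54 two-sided or 43 one-sided. The Protocol specifies two samples in any case.

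**The case against.** The arithmetic is not disputed; the objections concern cause, scope and weight.

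- **Cause.** The Protocol never says one-sided, so that reading is inferred from the match. A misprinted effect size could also give 82: with d = 0.44, a two-sided calculation gives 2 × 7.849 / 0.1936 = 81.1, so 82, and 80% power would hold for that larger effect. This is possible, but it requires the printed d to be wrong, whereas the one-sided reading uses every printed figure and lands on 82 exactly. Either way, d = 0.39, 80% power, 82 per group and a two-tailed 0.05 test cannot all be right.
- **Scope.** The 70% applies to 82 analysed per group. The Protocol plans both intention-to-treat and per-protocol analyses, and with complete data on all 196 the shortfall is only 2.5 points. That stands as a limit on the size. With the plan's own 20% loss, however, power falls below 70%.
- **SD.** Power to detect 1 log depends on an SD that the plan does not print. If the SD were 2.0 log, 82 per group would give about 89% two-sided power; at 3.0 log, about 56% (both SDs are assumptions). This is a good reason to state the SD, but the plan's 80% claim is tied to d = 0.39 and is wrong there.
- **Primary endpoint.** HBV DNA is the variable used for sizing, but it is not named as the sole primary endpoint. The criticism therefore concerns the comparison on which the trial was sized.
- **Weight.** The test is valid and the remedy is a wording change. That makes the fix cheap; it does not make the stated power correct.

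**Conclusion.** The concern holds. The Protocol's sample size meets its stated power only for a one-sided 0.05 test, and the SAP specifies a two-tailed one. At d = 0.39, two-sided power is 69.9% with 82 analysed per group, 77.5% if all 98 per group are analysed, and 67.7% if the allowed 20% are lost. The stated figure is 80%; reaching it two-sided would take 105 analysed per group.

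The result rests on the printed d, equal allocation and an unadjusted t-test. That the original calculation was one-sided is an inference from an exact match. The mismatch between the stated power and the planned test does not depend on that inference. The 2.56 log SD is derived from the printed difference and d, and is not stated in the plan; taking the log as base 10 is also an assumption.

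**What to change.** Keep the two-tailed test in the SAP and correct the sample-size paragraph in the Protocol. Suggested wording: *With 82 evaluable patients per group, a two-sided t-test at the 0.05 level has 70% power for d = 0.39, or 80% power for d = 0.44 (about 1.13 log10 IU/mL at the assumed SD).* State the SD that was used; it should be 2.56 log10 if the printed difference and d are both right. If d was misprinted, correct it there. It would also help to give the power at the number expected after exclusions (67.7% at 78 per group) and with everyone analysed (77.5% at 98 per group).

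The cost is a short text correction and a less favourable power figure, with no extra patients. Restoring 80% two-sided power by enlarging the trial would need 105 evaluable per group, which with 20% loss is 105 / 0.8 = 131.25, so 132 per group or 264 in total. That is not required in order to correct the statement. An analysis of log HBV DNA adjusted for its baseline value could recover some power, but the SAP does not plan one, and the documents give no baseline-to-follow-up correlation from which to put a figure on the gain.

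### A total of 196 does not keep 82 per group if 20% are excluded: about 78 per group remain, 196 covers only about 16% exclusion, and keeping 82 needs 206

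*Protocol*

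**What the plan says.** The sample-size paragraph is in the Protocol under Patients and study design. It starts from a t-test calculation ("The sample size was determined using two samples t-test power calculation") with a standardised difference of 0.39 ("Effect size (Cohen'd=0.39) was obtained using two parameters including difference and standard deviation"), power 0.8 and a significance level of 0.05. The result is: "The sample size was calculated out as 82 in each group". The next step adds the allowance for exclusions: "The ratio of exclusion was estimated as 20 %. Therefore, the sample size was set as 196 in this clinical trial". The same paragraph repeats the total as the enrolment target: "our study was designed to enroll 196 non-cirrhotic, HBV-infected patients".

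No inflation formula is shown, and no other reason for 196 is given.

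The same section describes two kinds of exclusion:

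- **Before randomisation.** "After obtaining written informed consent, levels of serum vitamin D, HBV DNA and quantitative HBsAg (qHBsAg) levels were measured", and patients are then excluded on those results.
- **After randomisation.** "Patients lost to follow-up or poor drug compliance (vitamin D intake amount < 80%) were excluded for per-protocol analysis". Both intention-to-treat and per-protocol analyses are planned.

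The SAP adds that "significance in all of the tests was two-tailed".

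**The concern.** The Protocol presents 196 as the consequence of 82 per group and 20% exclusion. On the usual reading, where 20% of those entered are excluded, it is not: removing a fifth of 196 leaves fewer than 164. A reader would believe that the trial can lose 20% and still have the calculated number in each group.

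The base of the 20% is also undefined. The text does not say whether the 196 are consented or randomised patients, or whether 82 is the target for the per-protocol or the intention-to-treat analysis. The reader therefore cannot tell which analysis the allowance protects.

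**Working it through.** **Inputs (Protocol, Patients and study design).** Effect size d = 0.39; power 0.80; significance level 0.05; 82 per group, so 164 in total; exclusion 20%; planned total 196. Equal allocation (98 per group) is an assumption: no ratio is stated, but a single figure for each group implies it.

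**1. Reproducing 82.** The exact two-sample t-test at d = 0.39 and one-sided 0.05 needs 81.98, so 82 per group. Two-sided, it needs 104.2, so 105. The 82 therefore rests on a one-sided test, while the SAP makes all tests two-tailed. That mismatch is a separate point. Both versions are shown below so that the effect of the inflation step can be seen alone.

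**2. Reproducing 196.** 164 × (1 + 0.20) = 196.8, which rounds down to 196 (per group, 82 × 1.2 = 98.4, so 98). By contrast, 164/(1 − 0.20) = 205. That 196 came from multiplying by 1.2 is an inference from the match.

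**3. What 196 delivers at 20% exclusion.** 196 × 0.80 = 156.8; 156.8/2 = 78.4, about 78 per group with equal loss.

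**4. What 82 per group requires.** 82/0.80 = 102.5, so 103 per group and 206 in total. The shortfall is 206 − 196 = 10 patients.

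**5. The exclusion that 196 can absorb.** 1 − 164/196 = 0.163, or 16.3%.

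**6. Effect on power (noncentral t, d = 0.39, level 0.05).**

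| Evaluable per group | One-sided | Two-sided |
|---|---|---|
| 82 vs 82 (target) | 80.0% | 69.9% |
| 78 vs 78 (20% excluded, equal loss) | 78.2% | 67.7% |
| 59 vs 98 (all 39 exclusions in one arm) | 76.2% | 65.3% |
| 98 vs 98 (no loss) | 85.9% | 77.5% |

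The last two rows are bounds. The 59 comes from 196 × 0.20 = 39.2, about 39, and 98 − 39 = 59. It is included because the intake criterion can apply only to the vitamin D arm, so per-protocol losses may be unequal.

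**7. Effect on the detectable difference at 80% power.** The Protocol equates 1 log with d = 0.39, so a detectable d converts to log10 units as d/0.39.

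- One-sided: d goes from 0.390 (82 per group) to 0.400 (78), or from 1.00 to 1.03 log10.
- Two-sided: d goes from 0.440 to 0.451, or from 1.13 to 1.16 log10.

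**The case against.** Four arguments can be made for the plan.

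- **The ratio may be excluded to retained.** Then 196/1.2 = 163.3 against 164, and the gap is only rounding. This reading is possible and cannot be ruled out. But 0.2/1.2 = 16.7% of those enrolled, which is not what a reader takes from a 20% exclusion figure, and the text does not say so. The wording needs correcting on this reading too.
- **Intention-to-treat may lose nobody.** If the 20% is only exclusion from the per-protocol set and every outcome is observed, intention-to-treat keeps 98 per group and power is above target one-sided (85.9%). This stands as a bound. However, patients lost to follow-up have no two-month value, the documents describe no handling of missing values, and nothing says which analysis the 82 is for. If the 20% means screening exclusions instead, about 157 still remain, below 164.
- **The effect is within the precision of the inputs.** An unrounded d between 0.385 and 0.395 moves one-sided power at 82 per group between 79.1% and 80.9%, as wide as the loss itself. That is fair, and it limits how much weight the point deserves. It does not make the arithmetic right.
- **The sidedness mismatch is larger and would replace 82, 196 and 206 together.** This is true: 206 restores the plan's own 82, not 80% power for a two-tailed test. The inflation step is still a distinct error and would carry over to any recalculated number.

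**Conclusion.** The concern holds. On the usual reading of a 20% exclusion rate, with equal groups and equal loss, 196 patients leave about 78 evaluable per group instead of 82. The plan is 10 patients short of 206 and covers 16.3% exclusion, not 20%.

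The cost attributable to this step is about 2 points of power (80.0% to 78.2% one-sided; 69.9% to 67.7% two-sided) and about 0.03 log10 in the detectable difference. The rest of the gap to 80% under the two-tailed test is due to sidedness and is not counted here.

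The arithmetic is certain. How 196 was derived, and what the 20% is a fraction of, are not stated. The statement should be corrected, but the effect is modest.

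**What to change.** Restate the paragraph without adding patients, for example:

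> The planned 196 patients (98 per group) allow for about 16% exclusion. With 20% exclusion and equal loss in both groups, about 78 per group are evaluable, giving power of 78% (one-sided 0.05) or 68% (two-sided 0.05) for d = 0.39.

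Keep only the power figure that matches the sidedness finally adopted, and confirm the equal allocation. If the ratio was meant as excluded to retained, say so and give it as 16.7% of those enrolled.

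The sponsor should also confirm two things:

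1. Whether the 196 and the 20% refer to consented or randomised patients. If consented, the exclusions made after the baseline measurements either use up part of the 20% or reduce the evaluable number further.
2. Whether 82 per group is the per-protocol or the intention-to-treat target.

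The cost is one rewritten paragraph and two clarifications. The analysis does not change. The stated allowance falls from 20% to about 16%, and the stated power by about 2 points from this correction alone.

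### The stated power of 0.8 is not established for the intention-to-treat comparison: the 20% allowance replaces excluded patients but makes no allowance for a diluted effect

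*Protocol*

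**What the plan says.** All the sizing text is in the protocol under Patients and study design. The method is given as "The sample size was determined using two samples t-test power calculation". The target is "The 1 log increase of serum HBV DNA level was defined as a significant difference between two samples", and "Effect size (Cohen'd=0.39) was obtained using two parameters including difference and standard deviation". The error rates follow: "The power and a significant level were set as 0.8 and 0.05, respectively". The result is 82 per group, raised as follows: "The ratio of exclusion was estimated as 20 %. Therefore, the sample size was set as 196 in this clinical trial". The 20% is not defined further, and the 0.8 is not tied to an analysis set.

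The same section later says "Patients lost to follow-up or poor drug compliance (vitamin D intake amount < 80%) were excluded for per-protocol analysis", and then "Both intention-to-treat and per-protocol analyses were conducted". Neither set is named as primary.

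The sizing text does not say whether the test is one- or two-sided. The SAP does: "significance in all of the tests was two-tailed and a p value of less than 0.05 was" (the sentence breaks off there in the text available).

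**The concern.** Adding patients is the right response to patients who leave an analysis. It does not correct for patients who stay in with less exposure. If a share a of the vitamin D arm is non-adherent and has no effect, the mean difference shrinks by the factor (1 − a), and keeping the same power needs a sample larger by 1/(1 − a)². At a = 0.20 that factor is 1.56. The plan's factor is 1.2, and d = 0.39 is carried unchanged into a trial that will also be analysed by ITT.

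The ITT comparison is the one that randomisation protects. If its power is below the printed figure, a null ITT result will be read as stronger evidence of no effect than it is, and a difference between the ITT and per-protocol results will be harder to interpret.

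**Working it through.** **Inputs from the documents.** d = 0.39; power 0.8; alpha 0.05; 82 per group; 20% exclusion; 196 in total; two-tailed tests (SAP). Equal allocation is taken from the equal group sizes, giving 196 / 2 = 98 per arm.

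**Inputs not given, so assumed.** L is the share lost in each arm and absent from the analysis. A is the share of the vitamin D arm that is non-adherent but analysed. r is the share of the effect those patients keep. The 1 log is taken as the effect in adherent patients.

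**Step 1: reproduce the plan's figure.** In a two-sample t-test with d = 0.39 and n = 82 per group, the noncentrality is 0.39 × √(82/2) = 2.50. Power is 80.0% one-sided and 69.9% two-sided. So 82 is reproduced only with a one-sided 0.05 test; 80% two-sided needs 105 per group. The total follows as 82 × 1.2 = 98.4, taken as 98, and 98 × 2 = 196.

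**Step 2: ITT power.** Patients analysed per arm: n = 98 × (1 − L). Diluted effect: d′ = 0.39 × [1 − A(1 − r)/(1 − L)]. Power comes from the noncentral t with noncentrality d′ × √(n/2). The SD is held fixed.

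| Case | n per arm | d′ | Two-sided | One-sided |
|---|---|---|---|---|
| No loss, no dilution | 98 | 0.390 | 77.5% | 86% |
| A = 10%, r = 0.5 | 98 | 0.3705 | 73% | 83% |
| A = 20%, r = 0.5 | 98 | 0.351 | 69% | 79% |
| L = 10%, A = 10%, r = 0 | 88.2 | 0.347 | 63% | 74% |
| A = 20%, r = 0 | 98 | 0.312 | 58% | 70% |

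For the fourth row, the diluted share among those analysed is 0.10/0.90 = 0.111, and 0.39 × 0.889 = 0.347. For the last row, 0.39 × 0.80 = 0.312.

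**Step 3: how much dilution the extra patients absorb.** Keeping excluded patients in ITT also raises n from 82 to 98. One-sided, 98 per arm still gives 80% at d′ = 0.356, a dilution of 1 − 0.356/0.39, or about 9%. With 20% non-adherent, that means keeping a little over half the effect (1 − 0.09/0.20 = 0.55). Two-sided, 80% at 98 per arm needs d = 0.402, above the planned 0.39, so there is no margin to absorb any dilution.

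**Step 4: per-protocol set.** Removing 20% from 98 leaves 98 × 0.8 = 78.4 per arm. At d = 0.39, power is about 68% two-sided and 78% one-sided. At 82 per arm it is 70% and 80%.

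**The case against.** The strongest reply is that the premise is partly inferred. The 20% is called only an exclusion ratio, and the section also uses exclusion for eligibility, including checks made after consent and blood testing. If the 20% covers screening failures, it implies no dilution. If it is all loss to follow-up with completers analysed, power is 68% two-sided and 78% one-sided through smaller numbers alone. The 1 log may also be meant as the difference between the groups as randomised, with non-compliance already counted. The text does not settle either point, and both objections stand as limits on the size of the effect.

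It can also be said that untreated controls cannot be non-compliant, so a 20% non-adherent vitamin D arm is only about 20 of 196 patients. That is correct, but it cuts both ways. If 20% is a whole-trial share made up of 10% lost and 10% non-adherent, all the non-adherence falls in the vitamin D arm, where it is 20%. With no effect in those patients, power is about 52% two-sided and 64% one-sided. The range in the table is therefore not a floor.

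A reader might infer that ITT power is below 80% whatever is assumed, even one-sided. The documents do not support that: one-sided power is 80.5% if 20% are non-adherent and keep 60% of the effect, and 83% if 10% keep half. The one-sided basis is itself only a back-calculation. Nor do they support the inference that a null ITT beside a positive per-protocol result is likely. In simulation of the last table row, that pattern arose in about 13% of trials one-sided and 16% two-sided.

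Finally, part of the two-sided shortfall comes from test sidedness. It alone takes the undiluted case to 77.5%. Dilution comes on top and would remain if the sidedness were corrected.

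**Conclusion.** The point holds in a limited form. The protocol's 0.8 is not established for ITT, because the plan does not say which set it covers and nothing in it allows for patients who stay in with less exposure. Under the SAP's two-tailed test no case examined reaches 80%. The loss attributable to dilution alone is between about 4 points (10% non-adherent keeping half the effect: 77.5% to 73%) and 19 points (20% non-adherent with none: 77.5% to 58%).

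These sizes rest on three assumptions that the documents neither confirm nor exclude: the split of the 20%, the effect kept by non-adherent patients, and the 1 log being the effect under adherence. This is an unstated planning assumption rather than a slip in arithmetic.

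A reader might also conclude that the 0.8 can simply be reassigned to the per-protocol set. It cannot: Step 4 shows that under the SAP's test the figure does not hold there either.

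**What to change.** In the protocol's sample-size paragraph:

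- Replace the unqualified 0.8 with the two-sided ITT power for 196 randomised, shown as a range (about 58% to 77.5%) over stated loss and non-adherence assumptions.
- Give the two-sided per-protocol power beside it: about 68% at 78 per arm, 70% at 82. Do not state that 0.8 holds for the per-protocol set.
- Split the 20% into loss to follow-up and non-adherence, and say whether each share refers to the whole trial or to the vitamin D arm. If the final split lies outside the cases in the table, recompute the range.
- Say whether the 1 log is the difference among adherent patients or among all randomised patients.

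The cost is wording and a short recalculation. Patient numbers need not change. The downside is a less favourable stated power.
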